**Version 1.8, Date: May 10, 2022**

## 1.0 PROJECT SUMMARY/ABSTRACT

Effective interventions that can address uncontrolled hypertension, particularly in underrepresented populations that use the emergency department (ED) for primary care, are critically needed.[1, 2] [3] **Uncontrolled hypertension (HTN)** contributes significantly to cardiovascular morbidity and mortality and **is more frequently encountered among patients presenting to the ED.** [4, 5] **EDs serve as the point of entry into the health care system for many high-risk patient populations, particularly minority and low-income individuals.**

Preliminary data from our research group, based on a largely minority patient population presenting to the ED, demonstrated significant rates of subclinical heart disease (diastolic dysfunction and left ventricular hypertrophy) in those with elevated blood pressures.[6] These early echocardiogram changes are reversible with existing strategies to improve blood pressure control making ED interventions within this population imperative. [7] [8]

The proposed project underscores the following: **1)** The prevalence of uncontrolled/undiagnosed HTN in underrepresented groups presenting to the ED is alarmingly high, and **2)** ED engagement and early risk assessment/stratification is a cost-effective, feasible innovation to help close health disparity gaps in HTN. This proposal involves a *two-arm randomized controlled trial of up to 770 patients from the Emergency Department at University of Illinois Hospital with elevated blood pressure (BP). The primary objective is to determine the effectiveness of an emergency department-initiated Educational and Empowerment (E) intervention with a Post Acute Care Hypertension Consultation (PACHT-c) intervention (arm 2) on the primary outcome of mean systolic blood pressure (SBP) differences between the two trial arms at 6-months post intervention. Secondary objectives include evaluating the effectiveness of this ED education and empowerment intervention on mean SBP and diastolic blood pressure (DBP) differences at 3-months, and mean DBP differences at 6-months. Additionally improvement in cardiovascular risk score (as measured by the Atherosclerotic Cardiovascular Disease (ASCVD) Risk Score), medication adherence (as measured by the Modified Morisky Scale), and primary care engagement (measured by compliance with outpatient follow-up appointments), will also be assessed as part of this study.*

## 2.0 BACKGROUND/SCIENTIFIC RATIONALE

**A. Background** - EDs serve a high-risk population that is not readily captured in other clinical settings with many patients utilizing the ED as part of their primary care access. [3, 9] Moreover, patients who report using the ED as their usual site of care are disproportionately more likely to have poor cardiovascular outcomes relative to private doctor's offices [10]

**Why Study Uncontrolled Hypertension in the Emergency Department Setting?** It is estimated that the prevalence of uncontrolled/undiagnosed hypertension in the ED is as high as 45%. [11] Hypertensive patients presenting to the ED are a particularly high-risk group with >50% having stage II or higher hypertension (SBP > 160 or DBP >100).[4] Many cases of elevated blood pressures in the ED are incidental findings and not related to the patient's chief complaints. Incidental hypertension represents a quandary for the emergency physician who cannot guarantee follow-up treatment.[12, 13] Thus identification and referral rates remain low in patients presenting to the ED with moderate BP elevations despite published outpatient guidelines. A recent study reported approximately 59% of men and 78% of women with elevated BP in the ED had continued elevated readings at outpatient follow-up after the ED visit. [14] Several studies have found that only 7-25% of ED patients with elevated BP are given instructions for outpatient BP follow-up. [12-14] Currently, **there is no risk assessment or stratification based upon blood pressure assessment performed on hypertensive patients prior to discharge from the ED.** All patients receive the same standard discharge instructions from the ED to follow up with a primary care provider (PCP). Recent emergency medicine literature suggests that if evidence-based guidelines were available for management of these patients and more assured follow-up mechanisms were in place, there would be greater compliance with referral guidelines and heightened awareness of secondary prevention interventions available to ED physicians. [11]

In 2010, there were 128 million ED visits, and by 2012, this number had increased to 138 million. [15] The proposed study is novel because it is initiated in the emergency department, is an innovative change to the current care delivery model, utilizes mobile health home BP monitoring, and can decrease the health disparity gaps associated with uncontrolled HTN. EDs serve as the point of entry into the health care system for many high-risk patient populations, particularly minority and low-income individuals, who are not readily captured in other clinical

settings because a significant number of these patients do not have a medical home and routinely utilize the ED as their source of primary care. EDs are well suited at the interface between inpatient and outpatient care and can contribute to reducing the health disparity associated with uncontrolled HTN in high-risk minority populations through focused engagement.

### **3.0 OBJECTIVE/AIMS**

The specific aims and hypotheses to be tested are:

**Aim 1:** Evaluate the effectiveness of an ED-based E + PACHT-c intervention (arm 2) on the primary outcome *of mean SBP difference* at 6-months post-intervention compared to usual care (arm 1).

H1: The mean SBP difference (from baseline) will be significantly greater in the E+ PACHT-c group (arm 2) compared to the usual care group (arm 1) at 6- months post-randomization, i.e., SBP change in arm 2 > arm 1 at 6-months post-randomization.

**Aim 2:** Evaluate the effectiveness of an ED-based E2 intervention with PACHT-c on the secondary outcome of mean SBP and DBP differences at 3-months and 12-months, and mean DBP differences at 6 months post-intervention compared to usual care.

H2: The mean SBP and DBP differences from baseline to 3- months and baseline to 12-months post-intervention and mean DBP at 6-months post intervention will be significantly greater in the ED-based E2 intervention compared to the usual care group, i.e., SBP and DBP change in arm 2 > arm 1 at 3 –months and 12-months post-intervention and DBP change in arm 2 > arm 1 at 6 -months post-intervention.

**Aim 3:** Examine if the E2 intervention reduces racial disparities. Specifically, if the intervention is as effective in racial minorities as non-minorities. This will be an exploratory analysis and will primarily focus on changes in cardiovascular risk score/profile. Also included will be an assessment of intervention mediators: primary care engagement, medication adherence, and HTN knowledge in these same patients at 3 and 6 -months post randomization-intervention.

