**Assessment of Impact of Intervention on the Racial Disparity Associated with Uncontrolled**

**HTN and Mediating Factors (Aim 3):** We will examine whether the intervention reduces racial disparities associated with uncontrolled HTN, i.e. is this intervention as effective in ethnic minorities as non-minorities. This will be an exploratory analysis and will primarily focus on changes in cardiovascular risk score. In addition, we will measure two potential mediating factors multiple times during the trial: **1)** adherence to follow-up visits, and **2)** the Modified Morisky Scale. All participants will receive phone calls at predetermined times to determine **primary care engagement**. All communication will be scripted and include: **1)** whether follow-up visits with the PCP have occurred or are scheduled; and **2)** the Modified Morisky Scale to assess current HTN medication use and understanding. The appropriate surveys will be administered by RAs at the time of enrollment, by phone at 1 and 5 months, and at 3 and 6 months during the in-person visit. Shorter calls will be made at 2, 5, and months to schedule the 3 and 6-month appointments.

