*Aim 2:* We hypothesize that the mean change in SBP and DBP at 3 and 12 months and mean DBP at 6 months after randomization will be higher in the intervention arm compared to usual care. Linear regression models will be used to compare change in continuous BP between treatment arms at 3 months and DBP at 6 months; mixed effects linear regression models will be used to combine the two-time points into a single model.

*Aim 3:* Change in the cardiovascular risk score at 3 and 6 months will be analyzed to assess racial disparity by testing the interaction between a binary indicator of treatment group and a binary indicator of minority versus non-minority. The distribution of change scores will be examined to determine whether linear regression is appropriate; if not, ordinal categories will be defined and proportional odds logistic regression will be used. Models will be fit at each of 3

and 6 months, and mixed-effects models will be used to combine the two-time points into a single model.

*Handling Missing Data:* For the missing data analysis an ITT will be implemented. Furthermore, missing data will be handled by using a mixed-effects model approach, which assumes that the data is missing at random and hence will not bias the analysis. If we determine that data may not be randomly missing and thus non-ignorable then two well accepted approaches to handle this situation will be implemented, namely selection models and pattern mixture models.

*Other Statistical Considerations:* Sampling balance for the key predictors will be checked and adjusted for in the analysis, and their mediating and moderating effects will be examined if needed. We address power for Aims 1 and 2 for unadjusted tests. Adjustment for covariates will decrease power slightly by using up degrees of freedom, but the adjustment will also create more accurate estimates, so the expected power will be similar.

Effect Size		80% Power		85% Power	
Standardized	mmHg*	Sample Size		Sample Size	
	DBP	SBP	N	N**	N
0.20	2.40	4.20	786	1049	898
0.25	3.00	5.25	504	673	576
0.30	3.60	6.30	350	467	400
0.35	4.20	7.35	258	345	294
0.40	4.80	8.40	198	265	178

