0.45	5.40	9.45	156	209	178
0.50	6.00	10.5	126	169	144
*Effect size is defined as difference in means divided by standard deviation. From our pilot study: DBP Standard deviation 12 mmHg; SBP Standard Deviation 21 mmHg.					
**25% attrition is assumed and thus required sample size, N**, is obtained by dividing calculated sample size, N, by 0.75.					

*Sample Size:* The primary hypothesis of the study is that the difference in systolic blood pressure from baseline to month 6 is different across the two treatment arms. Testing this hypothesis amounts to testing difference in mean systolic blood pressure between the two treatment groups at 6 months, due to randomization (since the mean SBP at baseline is the same across groups). Thus, sample size estimation is determined by comparing

the mean SBP at 6 months using a two-sample, two-sided, 5% significance t-test with 80% and

85% statistical power. Sample size is calculated first to detect a pre-determined effect size (difference in means divided by standard deviation) and then converted to blood pressure units, namely mmHg. Data from our pilot study resulted in estimates of DBP standard deviation of 12 mmHg and SBP standard deviation of 21 mmHg. For example, the required sample size to detect an effect size of 0.25 ( $0.25*12 = 3$  mmHg in DBP, and  $0.25*21 = 5.25$  mmHg in SBP) is 504 for 80% power and 576 for 85% power, using a two-sided, two-sample 5% significance t-test. An attrition-adjustment to the calculated sample size give 673 and 770 patients for 80% and 85%, respectively.

*The statistical analysis:* Mean BPs will be compared across groups using a two-sample, two-sided, 5% significance t-test. The analysis will be then extended to gain statistical power by adjusting the comparison by baseline BP levels. An intention-to-treat analysis will be undertaken by using mixed effects models so that all the available information on each patient is used for the analyses. Further analyses using maximum likelihood estimators for data imputation and weighting will be implemented to better account for missing data. Moreover, key variables (age, sex, race/ethnicity) will be compared across treatment groups and if different will be used in a multivariate mixed effects model.

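### Aim 3 defines reducing racial disparities as equal effectiveness, but on the difference scale of the planned models equal effects leave the gap unchanged

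*Combined protocol and SAP*

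**What the plan says.** Section 3.0 states Aim 3 as: "Examine if the E2 intervention reduces racial disparities. Specifically, if the intervention is as effective in racial minorities as non-minorities". Section 12.0 restates the aim in the same terms. The Aim 3 paragraph of section 6.0 says the trial will examine whether disparities are reduced and explains this, after an 'i.e.', as the question "is this intervention as effective in ethnic minorities as non-minorities". In all three places, equal effectiveness serves as the definition of reduced disparity.

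The analysis is in section 12.0. Change in cardiovascular risk score at 3 and 6 months is to be used to assess racial disparity by "testing the interaction between a binary indicator of treatment group and a binary indicator of minority versus non-minority". Linear regression is planned, with proportional odds on ordinal categories as a fallback if the distribution of change scores is unsuitable. Mixed-effects models then combine the two time points.

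The status of the aim is clear: "This will be an exploratory analysis and will primarily focus on changes in cardiovascular risk score/profile". On power, section 12.0 says "We address power for Aims 1 and 2 for unadjusted tests", so Aim 3 has no power statement. Aims 1 and 2 have directional hypotheses (H1 and H2). Aim 3 has no hypothesis, no direction that would count as a reduction, no similarity margin and no rule for turning the interaction into a conclusion.

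**The concern.** A disparity is a gap between groups. If both groups gain equally, both improve and the gap stays where it was. Narrowing it requires the worse-off group to gain more, which is an interaction in one particular direction. The plan names the right quantity, the interaction, but ties the disparity claim to the value of that quantity at which the gap does not move.

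What is at stake is the reading of Aim 3. A null interaction fits the stated criterion, and nothing in the plan stops it from being described as reduced disparity. Closing disparity gaps is a central part of the rationale in sections 1.0, 2.0 and 4.3, so readers are likely to look to Aim 3 for that conclusion.

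**Working it through.** **1. The plan's own figure.** Section 12.0 says the sample size for an effect size of 0.25 "is 504 for 80% power and 576 for 85% power, using a two-sided, two-sample 5% significance t-test". With the normal approximation, n per arm = 2(z₀.₉₇₅ + z_power)² / 0.25².
- 80% power: 2(1.960 + 0.842)² / 0.0625 = 251.2, so 252 per arm and 504 in total.
- 85% power: 2(1.960 + 1.036)² / 0.0625 = 287.3, so 288 per arm and 576 in total.
- Attrition: the table footnote says "25% attrition is assumed and thus required sample size" comes from dividing by 0.75. This gives 504/0.75 = 672 and 576/0.75 = 768, against the stated 673 and 770. The difference is immaterial.

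These figures serve the blood pressure comparison. No figure is stated for Aim 3.

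**2. The logical point.** Let M and W be the usual-care means in minority and non-minority patients, and e_M and e_W the intervention effects.
- Gap in arm 1 = M − W.
- Gap in arm 2 = (M + e_M) − (W + e_W).
- Change in gap = e_M − e_W, which is the arm-by-minority interaction.

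The starting gap cancels. Modelling change from baseline gives the same interaction in expectation, because randomisation makes the baseline gap the same in both arms. Equal effectiveness means e_M = e_W, so the change in gap is zero.

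**3. Illustration.** The usual-care means of 150 and 145 mmHg are assumed. The 5.25 mmHg effect is 0.25 × 21 from section 12.0, and the unequal effects are multiples of it.

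| Effect in minorities | Effect in non-minorities | Gap, arm 1 | Gap, arm 2 | Change |
|---|---|---|---|---|
| −5.25 | −5.25 | 5 | 144.75 − 139.75 = 5.0 | 0 |
| −7.875 | −2.625 | 5 | 142.125 − 142.375 = −0.25 | −5.25 |
| −5.25 | −7.875 | 5 | 144.75 − 137.125 = 7.625 | +2.625 |

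The first row meets the plan's criterion, and the gap does not move. The second row narrows the gap but fails the criterion.

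**4. Precision, as a guide only.** The documents give "estimates of DBP standard deviation of 12 mmHg and SBP standard deviation of 21 mmHg" but no SD for the risk score and no minority share beyond saying that minority patients predominate. I therefore work in SD units over assumed minority shares p, with 576 analysed, 1:1 allocation within each group, a common SD and no covariate adjustment. SE = √(4/(Np) + 4/(N(1−p))). The detectable difference is (1.960 + 0.842) × SE. Power for an interaction of 0.25 SD is Φ(0.25/SE − 1.96).

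| p | SE (SD units) | 95% CI half-width (SD units) | Same on SBP, SD 21 | Detectable at 80% power | Power for 0.25 SD |
|---|---|---|---|---|---|
| 50% | 0.167 | 0.327 | 6.9 mmHg | 0.467 SD | 32.3% |
| 80% | 0.208 | 0.408 | 8.6 mmHg | 0.584 SD | 22.4% |
| 90% | 0.278 | 0.544 | 11.4 mmHg | 0.778 SD | 14.5% |
| 95% | 0.382 | 0.749 | 15.7 mmHg | 1.071 SD | 9.6% |

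Every half-width exceeds the 0.25 SD planning effect. Under these assumptions a non-significant interaction is likely even if the effects differ by as much as the whole planned effect. It would show neither equality nor a narrower gap. Step 2 does not depend on this table.

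**The case against.** The best defence is that the analysis is already right. The arm-by-minority interaction is exactly the difference in gaps between arms, so correcting the criterion leaves the model as it is. That stands: a reader might infer that Aim 3 needs a different analysis, and it does not.

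A reader might also infer that the sponsor intends to report a null interaction as reduced disparity. No section says so. Aim 3 has no hypothesis and no reporting rule; the wording only leaves that misreading open.

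Nor is the criterion wrong on every scale. Under the proportional-odds fallback, the same odds ratio applied to groups with different starting risk can change the absolute gap. The result here is for the difference scale, which is that of the planned linear models.

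Sections 1.0 and 2.0 suggest another route: if emergency departments reach minority patients whom other settings miss, an equally effective intervention could narrow a population gap through reach. This makes equal effectiveness a sensible question, but Aim 3 does not state that reading, and a single-site emergency department trial has no data on the population gap.

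Finally, the aim is exploratory, and a rule based on a CI can look too confirmatory for it. The label limits how strong a conclusion may be. It does not repair a criterion that describes the absence of the claimed result.

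**Conclusion.** The point holds for the criterion and its missing decision rule. On the difference scale, the stated criterion corresponds to a change in gap of exactly zero, whatever the starting gap, so meeting it cannot support a claim of reduced disparity. No other section supplies a direction or rule that corrects this.

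Reading greater benefit in minorities as a narrower gap assumes that minority patients have the worse outcome under usual care, as the plan's rationale implies; reporting the gap by arm would show it. The SBP half-widths might be taken as the precision of Aim 3, but the documents do not support that: its outcome is the risk score, whose SD is not given, and the minority shares are assumed. They are illustrative. Aims 1 and 2 and the sample size are unaffected. The change is worth making, but its reach is limited to one exploratory aim.

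**What to change.** Choose one of two wordings and apply it in sections 3.0, 6.0 (Aim 3 paragraph) and 12.0.

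- **Keep the disparity aim.** Retain the interaction on change in cardiovascular risk score. Define it as the minority minus non-minority gap in arm 2 minus the same gap in arm 1. Report the gap in each arm and the interaction with its 95% CI, labelled exploratory. State that only an interaction in the direction of greater benefit in minorities, with a CI excluding zero, supports the statement that disparities were reduced. Otherwise the conclusion is that the gap was not shown to change. If the ordinal fallback is used, say on which scale the gap is judged.
- **Rename the aim.** Ask whether the effect is similar in minority and non-minority patients and drop the disparity-reduction claim. Report the interaction with its CI, and state a margin in advance if similarity is to be claimed.

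The cost is an amendment to wording, with no new data, visits or participants. The downside of the first option is that a disparity claim becomes harder to make; if the precision is anything like that illustrated, the likeliest conclusion is that the gap was not shown to change.

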**Table 1: Intervention Components by Arm \***

Arm 1: Usual Care (N=385)				
Arm 2: E Intervention (N=385)				
Intervention Components by Arm	Baseline	Quarterly	Mid-point	End
Location	ED	Phone	UI-Health Suite 1600	UI-Health Suite 1600
Time Point in Months (0=ED discharge)	0	1, 3, 5	3	6
Duration	10-20 min	5 min	10-20 min	20 min
BP Measured	1, 2		1, 2	1, 2
Clinical Data (from med chart)	1, 2			

Atherosclerotic Cardiovascular Disease (ASCVD) Risk Score	1,2			1,2
Hypertension Knowledge Assessment	1, 2			1, 2
Modified Morisky Scale	1, 2	1, 2	1, 2	1, 2
Patient Activation Measurements Survey (PAM)	1, 2	1, 2	1, 2	1, 2
Verify patient contact info	1, 2	1, 2	1, 2	
Bedside Echocardiogram Education	2			
Hypertension Education Video	2			
PACT-Hypertension (Pharmacy) Consultation:	2			
Home BP Monitoring Training and Reminders	2	2	2	

\*We may ask participants to return for a follow up at one year post-enrollment at which time all assessments and surveys performed at recruitment will be repeated.

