## **12.0 STATISTICAL CONSIDERATIONS**

### ***Outcomes, Analysis Methods and Sample Size***

**Statistical Analysis Plan:** Outcome analyses will be conducted within the UIC Institute for Minority Health virtual environment. Descriptive statistics will be used to assess completeness of study data, normality of outcome measures, and potential covariates as well as to identify potential covariate imbalances between study arms. Based on our pilot study work and our protocol, which emphasizes repeated telephone contacts with participants' post-baseline, we anticipate relatively low loss to follow up at 3 and 6 (at most 20%). For the primary analysis of each study hypothesis we will initially adopt an "intention to treat", (ITT) modality. We will apply the independent samples t-test and Chi-squared test to compare key measures between

treatment arms to ascertain balancing of important measures that may have an influence on the outcome variables. All statistical analysis will be conducted using SAS 9.4 (SAS Institute Inc., Cary, NC, USA) and R version 3.3.1. A brief description of the analytical plan by specific aim follows:

Aim 1: Evaluate the effectiveness of an ED-based E intervention with PACHT-c intervention (arm 2) on the primary outcome of *mean SBP difference* at 6 -months post-intervention compared to usual care (arm 1).

Aim 2: Evaluate the effectiveness of an ED-based E intervention with PACHT-c on the secondary outcome of *mean SBP and DBP differences* at 3-months and 12-months and *mean DBP differences* at 6 months post-intervention compared to usual care.

Aim 3: Examine if the E intervention reduces racial disparities. Specifically, if the intervention is as effective in racial minorities as non-minorities. This will be an exploratory analysis and will primarily focus on changes in cardiovascular risk score/profile. Also included will be an assessment of intervention mediators: primary care engagement, medication adherence, and HTN knowledge in these same patients at 3 and 6 months post randomization-intervention

*Aim 1:* We hypothesize that the mean change in SBP at 6 months after randomization will be higher in the intervention arm compared to usual care. Linear regression models will be used to compare change in continuous BP between treatment arms at 6 months; mixed effects linear regression models will be used to combine the two-time points into a single model.

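### Aim 3 names HTN knowledge as a mediator at 3 and 6 months, but Table 1 schedules the survey only at baseline and month 6, so its one follow-up value coincides with the 6-month outcomes

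*Combined protocol and SAP*

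**What the plan says.** Section 3.0 names three mediators for Aim 3 and gives their times: "primary care engagement, medication adherence, and HTN knowledge in these same patients at 3 and 6 -months post randomization-intervention". Section 12.0 repeats this: "primary care engagement, medication adherence, and HTN knowledge in these same patients at 3 and 6 months post randomization-intervention".

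In Table 1 the row reads "Hypertension Knowledge Assessment 1, 2 1, 2". The two entries are in the Baseline and End columns, which are months 0 and 6. The phone column (months 1, 3 and 5) and the Mid-point column (month 3) are empty. The Modified Morisky and Patient Activation (PAM) rows are filled in all four columns.

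The Aim 3 procedure paragraph in section 6.0 says: "In addition, we will measure two potential mediating factors multiple times during the trial". It then lists follow-up attendance and the Modified Morisky Scale, but not knowledge. Later it says that surveys will be given at several contacts, including the 3- and 6-month visits, without saying which surveys.

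The description of the knowledge survey under the ED screening details gives no follow-up times. The sentence there that schedules surveys at 3, 6 and 12 months closes the Morisky and PAM paragraph.

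**The concern.** To support a claim that the intervention worked through knowledge, knowledge has to be measured after the intervention and before the outcome it is meant to explain. Table 1 places the arm 2 video, echocardiogram clips and consultation at month 0 only. The continuing text messages are aimed at adherence to medication and to BP measurement. Month 3 is therefore the natural point at which to look for an effect of the education on knowledge, and the aim names it.

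If the survey is first repeated at month 6, it is taken at the same visit as the 6-month SBP and ASCVD score. An association between knowledge and those outcomes could then reflect knowledge improving control, or participants who gained control learning more along the way. At stake is whether the trial can say anything about the route by which the educational component acts. A month-3 score that is not collected cannot be recovered later.

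**Working it through.** The plan states no figure on this point, so the check sets the schedule against the aim.

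**Step 1. Schedule from Table 1 (both arms).**

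| Assessment | Month 0 | Phone 1, 3, 5 | Visit month 3 | Visit month 6 |
|---|---|---|---|---|
| HTN knowledge | yes | – | – | yes |
| ASCVD score | yes | – | – | yes |
| BP | yes | – | yes | yes |
| Modified Morisky | yes | yes | yes | yes |

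The mismatch does not depend on how the table's columns were read. Baseline, month 3 and month 6 would need three entries, and the knowledge row has two.

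**Step 2. Time points after baseline and before month 6.**
- HTN knowledge: 0
- ASCVD score: 0
- BP: 1 (month 3)
- Modified Morisky: 3 (months 1, 3 and 5)

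**Step 3. What same-visit data can and cannot show.** As an illustration, take 576 participants analysed (288 per arm; the plan's total before attrition for 85% power) and a standardized arm effect of 0.25. Mediation is declared when both the arm-to-knowledge coefficient and the knowledge-to-outcome coefficient (adjusted for arm) exceed 1.96 standard errors. The slope d linking knowledge and BP is not in the documents. It is assumed to be 0.2, 0.4 or 0.6, with 2,000 simulated trials each.

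| d | True path arm → knowledge → BP | True path arm → BP → knowledge only |
|---|---|---|
| 0.2 | 84.4% | 8.8% |
| 0.4 | 85.3% | 20.8% |
| 0.6 | 85.2% | 34.0% |

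The last column can be checked by hand, because the arm-to-knowledge test is the limiting one. The arm difference in knowledge is 0.25d, and its standard error is √(1 + d²) × √(2/288) = √(1 + d²) × 0.0833.
- d = 0.2: 0.05/0.0850 = 0.59, so the chance of exceeding ±1.96 is about 9%.
- d = 0.4: 0.10/0.0898 = 1.11, about 20%.
- d = 0.6: 0.15/0.0972 = 1.54, about 34%.

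Under the reverse path knowledge has no effect on BP at all, yet the same-visit test still declares mediation in roughly 9% to 34% of trials. These rates depend on the assumed slopes. The absence of time order in the data does not.

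**Step 4. Effect of the change.** A month-3 survey raises the count in Step 2 for knowledge from 0 to 1 and supplies the 3-month value that the aim names. The sample size does not change.

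**The case against.** **Table 1 may not be the controlling text.** Sections 3.0 and 12.0 both say 3 months, and the unnamed surveys in section 6.0 could include knowledge. Table 1 is also out of step elsewhere: it has no month-3 ASCVD score, although section 12.0 plans to analyse risk-score change at 3 months. This stands in part. A reader might infer that a 3-month assessment is impossible, or that no participant will have a month-3 score. The documents support only that none is scheduled in Table 1 and that the texts disagree.

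**Two factors measured repeatedly need not mean only two mediators.** This is fair. That sentence fits Table 1, where knowledge has a single follow-up value. It still conflicts with an aim that gives knowledge two follow-up times.

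**Month-6 knowledge would precede 12-month BP, which is an Aim 2 outcome.** This is true if the visit takes place. The footnote to Table 1 makes the one-year return optional, and 12 months lies outside Aim 3's stated window.

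**The two directions are not equally likely.** A reader might infer that a month-6 association would be just as consistent with reverse order. Nothing in the documents supports equal weight, and the rates in the working show ambiguity rather than parity.

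**The remedy is partial.** BP is also measured at month 3, so month-3 knowledge would coincide with that reading. Mediator-outcome confounding would also remain. Both points stand and should be stated in the plan.

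**Aim 3 is exploratory, focuses mainly on the risk score, and specifies no mediation model.** This stands as a limit on weight. It does not remove the gap between a stated assessment and the schedule.

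**Conclusion.** The point holds in a bounded form. One of three named mediators has no scheduled value at one of its two stated follow-up times. Within the 6-month schedule, its only post-baseline value is taken at the same visit as the 6-month SBP and ASCVD score, so it cannot establish that knowledge changed before those outcomes. This assumes that sites follow Table 1 rather than reading the survey into the unspecified wording of section 6.0.

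A reader might go further and infer that the trial can say nothing about knowledge, or that its main result is weakened. Neither follows. Randomization still allows the effect of arm on 6-month knowledge to be estimated; only the step from knowledge to outcome is weakened. The primary SBP comparison, Aim 2 and the sample size are untouched. The change should be made because it is cheap and the data are otherwise lost, but it concerns an exploratory aim.

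**What to change.** 1. In Table 1, add the 10-item knowledge survey at the month-3 visit for both arms.
2. Align the Aim 3 paragraph of section 6.0 with sections 3.0 and 12.0: say whether there are two or three mediators, and name the surveys given at each contact.
3. In section 12.0, prespecify that exploratory mediation of 6-month outcomes uses month-3 knowledge. State that this gives order only relative to month-6 outcomes, not to month-3 BP, and does not remove mediator-outcome confounding.
4. In the same edit, reconcile the missing month-3 ASCVD score in Table 1 with the 3-month risk-score analysis in section 12.0.

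The cost of item 1 is one table cell, one repeated REDCap form and a few minutes at an existing 10–20 minute visit where two surveys are already given. It also adds one more exposure to the same items before month 6, in both arms. Because scores are grouped as 7 or below, 8, and 9–10, one remembered item can move a participant up a category. That is a reason to analyse the total score as well.

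If month 3 is not added, remove HTN knowledge from the mediators in sections 3.0 and 12.0 and report it as a 6-month outcome compared between arms.
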